3.1 Screening/Covariate Measures

Demographics and Smoking History. Standard questionnaires will be self-administered at the Intake visit to collect the following data: demographics (age, gender, marital status, education), age at smoking initiation, cigarette brand, length of prior abstinence periods and current smoking rate. The Fagerstrom Test for Nicotine Dependence (FTND) will also be administered. The FTND is a 6-item, self-report measure of nicotine dependence derived from the Fagerstrom Tolerance Questionnaire [37]. The FTND scale has satisfactory internal consistency (Cronbach's $\alpha = .64$) and high test-retest reliability ($r = .88$) [38].

Medical History. A medical history (self-report) and a physical examination will be conducted at the Intake visit to review for any contraindications listed previously. The medical history (including height and weight) will be completed by a research staff member.

Psychiatric History. Current major depression, lifetime prevalence of psychosis, bipolar disorder, schizophrenia, hypomanic/manic episodes, and substance abuse will be determined via self-report during the phone screen and via semi-structured interview using the Mini International Neuropsychiatric Interview (MINI). The MINI is a 10-15 minute structured interview developed by the World Health Organization to assess major DSM-IV Axis 1 psychiatric diagnoses. This instrument permits both current (past 30 days) and lifetime assessments of psychiatric illness, and recent data support its reliability and validity [39]. The MINI will be administered by a trained research staff member at the Intake visit. There will be 100% review of paper MINIs by [name], a clinical psychologist with relevant training, to maintain quality control.

Suicidal Behavior and Ideation (C-SSRS). All participants will complete the C-SSRS (Screening Version) with a trained staff member at the Intake Visit. The C-SSRS is a structured interview that assesses the suicidal behavior and suicidal ideation in subjects [40, 41]. Occurrence of lifetime suicidal behavior is defined as having answered “yes” to at least 1 of the 4 suicidal behavior sub-categories (actual attempt, interrupted attempt, aborted attempt, and preparatory acts or behavior). Current suicidal ideation is defined as having answered “yes” to at least 1 of the suicidal ideation sub-categories (wish to be dead, non-specific active suicidal thoughts, active suicidal ideation with any methods without intent to act, active suicidal ideation with some intent to act [without specific plan], and active suicidal ideation with specific plan and intent) over the past month.

Urine Drug Screen. The urine drug screen will be administered at Intake and the last visit of each baseline week (Friday of weeks 1 and 5). The urine drug screen requires about 30ml of urine and indicates whether the subject has recently taken any exclusionary drugs (marijuana, cocaine, PCP, amphetamines, methamphetamines, tricyclic antidepressants, ecstasy, opiates, methadone, benzodiazepines, and barbiturates). Participants with a positive urine drug screen for any substance listed above will be deemed ineligible. In an effort to remain CLIA-compliant, results from urine drug screening will not be shared with participants. Participants will be informed that the testing is for research purposes only and that they will be informed of their eligibility status, but not of the specific testing results.

Urine Pregnancy Test. At the Intake and the last visit of each baseline week (Friday of weeks 1 and 5), participants will be supplied with a simple, CLIA-waived urine pregnancy screen and informed that pregnant women are not advised to participate in this research study. Participants will then be instructed to administer the pregnancy test independently and will inform study staff if they would like to continue participation after they have administered the pregnancy screen. Participants will be informed that there is no penalty for discontinuing participation at this point in the visit and that they will still receive travel reimbursement for the visit.

Breath Alcohol Concentration. The breath alcohol concentration (BrAC) assessment will be administered at the Intake visit and all subsequent study visits. The breath alcohol monitor assesses expired breath for alcohol content. A reading greater than or equal to 0.01 at any session indicates alcohol consumption within the last 14 hours and will result in the participant being withdrawn from the study.

Activity (Week #)	Intake	Baseline (1 & 5)			Quit Assessment (2 & 6)				
Day	0	Mon	Wed	Fri	Mon	Tue	Wed	Thu	Fri
TREATMENT									
Ramelteon (RAM) or Placebo					X ^a	X ^a	X ^a	X ^a	X ^a
Transdermal Nicotine (TN)					X	X	X	X	X
SCREENING/COVARIATES									
Demographics	X								
Smoking History/FTND	X								
Medical/ ETOH History (self-report)	X								
Psychiatric History (Self-report and MINI)	X								
Suicidal Behavior/ Ideation (C-SSRS)	X								
Urine drug/pregnancy screen	X			X					
Breath alcohol	X	X	X	X	X	X	X	X	X
Blood pressure	X	X	X	X	X	X	X	X	X
Blood draw (liver function tests) ^b	X								
Brief counseling				X					
TREATMENT VARIABLES									
Concomitant Medication Review	X	X	X	X	X	X	X	X	X
RAM Adherence (pill count)					X	X	X	X	X
TN Adherence					X	X	X	X	X
Side Effects (TN and RAM)		X	X	X	X	X	X	X	X
INTERMEDIATE OUTCOMES									
Sleep Diary		X	X	X	X	X	X	X	X
Pittsburgh Sleep Quality Index (PSQI)		X	X	X	X	X	X	X	X
Sleep efficiency (SensewearPro)		X	X	X	X	X	X	X	X
Depression Symptoms (CESD)	X			X					X
Withdrawal, Craving, Affect		X	X	X	X	X	X	X	X
SMOKING OUTCOMES									
Cessation/Smoking Rate (TLFB)	X	X	X	X	X	X	X	X	X
Carbon Monoxide (CO) Test	X	X	X	X	X	X	X	X	X
Note. No visits or assessments during washout (weeks 3-4). FTND=Fagerstrom Test for Nicotine Dependence; CESD= Center for Epidemiological Studies on Depression; TLFB=Timeline Followback a study medication taken the previous night; b only for those with a history of jaundice/liver disease									

Blood Pressure. At the Intake, participants presenting with elevated blood pressure (i.e., systolic blood pressure greater than 159 and/or diastolic blood pressure greater than 99) will have a second blood pressure reading taken after a ten minute period in which the participants will be instructed to sit comfortably. If, after the second reading the SBP is greater than 159 mmHg and/or the DBP is greater than 99 mmHg, the individual will be instructed to sit comfortably for 10 minutes and then have a third blood pressure reading. If, after the third reading the SBP is greater than 159 mmHg and/or the DBP is greater than 99 mmHg, the individual will be ineligible to participate.

Blood pressure will be measured at all subsequent in-person visits. If participants present with elevated blood pressure (i.e., systolic blood pressure greater than 159 mmHg and/or diastolic blood pressure greater than 99 mmHg) at any subsequent visit, the staff will follow the same steps listed above. If, after a third reading, systolic blood pressure remains greater than 159 mmHg and/or diastolic remains greater than 99 mmHg, the subject will be told to not take the next dose of study medication. If a participant presents with a SBP between 151-159 mmHg and/or DBP between 91-99 mmHg at the Intake or any visit during a Baseline week, the research staff will inform the participant that they have mild, Stage I, hypertension and advise they consult with a physician. The participant will remain eligible for the study and receive nicotine patches as scheduled. The research staff will notify the Study Physician/Health Care Provider who will review the blood pressure reading and determine whether it is safe for the subject to continue. Research staff will follow up with the participant accordingly.

Liver Function Tests and Gamma-glutamyl Transpepsidase. Only individuals with a history of jaundice/liver disease will provide a blood sample for liver function tests. One 8.5ml blood sample will be drawn at the Intake visit to conduct liver function tests. Blood will be collected and placed in a serum-separator tube (SST) and mixed thoroughly. Samples will be centrifuged at 3000 rpm for 15 minutes. The following chemistry will be assessed:

1. Total protein.
2. Albumin.
3. Globulin.
4. Albumin:Globulin ratio.
5. Bilirubin (total, conjugated and unconjugated)
6. Aspartate amino transferase (AST).
7. Alanine amino transferase (ALT).
8. Alkaline phosphatase (AP).
9. Gamma glutamyl transferase (Gamma-GT).

Brief counseling. These 20-minute sessions will occur during the final visit of each Baseline week (Friday). This counseling session will be similar to previous studies in our center (IRB#815789). Specifically, a trained smoking cessation counselor will review reasons for smoking and common withdrawal symptoms. Counselors will work with participants to develop plans to manage triggers, avoid cigarettes, and gather social support. Participants will also be taught a breathing relaxation technique for handling stressful situations.

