- Telephone Screening. Individuals interested in participating will be screened by an experienced research technician to determine initial study eligibility. If the subject meets preliminary phone eligibility and is interested in participating, he/she will be invited to attend a 2.5-hour Intake visit. Subjects will be contacted via phone call, text message, e-mail, and/or postal mail to remind them about their scheduled intake visit date and time. Method of preference will be collected over the phone.
- Intake (Week 0). In this 2.5-hour visit, participants will have their eligibility confirmed (using the previously detailed inclusion/exclusion criteria listed above). A schedule of activities for the day include:
 1. Arrive at the CIRNA and hear detailed description of the study and have any questions answered by a staff member from the CIRNA
 2. Complete combined study consent/HIPAA form
 3. Provide urine specimens for drug and (if applicable) pregnancy tests. Participants who test positive for either the urine drug screen and/or pregnancy test will be ineligible.
 4. Provide CO breath sample. Participants must have CO readings greater than or equal to 10ppm in order to be eligible for the study
 5. Provide BrAC measurements. Participants must have readings less than 0.01 in order to be eligible for the study
 6. Provide a blood pressure reading (See Blood Pressure Procedures under Screening/Covariate Measures)
 7. Complete routine medical history (self-report) with a member of the research staff
 8. Complete a psychological interview (MINI) and the C-SSRS with a trained research staff member (Description under Screening/Covariate Measures)
 9. Complete brief physical examination (led by a medical professional)
 10. Have height and weight measured (led by study staff)
 11. For individuals who report a history of jaundice/liver disease: provide an 8.5ml blood sample drawn for the assessment of liver function (LFTs and GGT enzyme levels). They will receive final confirmation of eligibility via phone call based on the liver function tests.

If a participant is ineligible due to any of the above criteria during the Intake, he/she will only be compensated \$10 for travel. However, if a participant tests positive for study prohibited drugs, he/she will not receive any compensation.

Otherwise, if a participant meets the above eligibility criteria at the Intake, he/she will be asked to complete the following:

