12. Complete questionnaires (demographics, nicotine dependence, smoking rate, withdrawal, and smoking urges)
13. Receive instructions on how to record their daily sleep diaries and report their sleep and wake times
14. Be randomized to receive RAM or PLA during the first phase
15. Finalize their study schedule

Participants will be asked to refrain from using any study prohibited drugs (note: participants are allowed to take prescription medications not in the exclusion list) throughout their participation in the study. Female participants will also be asked to use an approved method of contraception through the study.

- Final Eligibility Phone Call (only for individuals with a history of jaundice/liver disease). When liver function tests have been reviewed and authorized by the Study Physician, a study staff member will call the subjects to inform them of their final eligibility.

Final Eligibility is defined as: Liver function test results and GGT liver enzyme levels that are no more than 20% outside the normal, clinical range. Albumin/Globulin ratios 20% outside of normal range will be evaluated for clinical significance by the Study Physician and eligibility will be determined on a case-by-case basis.

Ineligible subjects may be referred to other studies at our center. Eligible subjects will schedule all other study visits and be randomized to receive RAM or PLA during the first phase. During the first study visit, participants will receive instructions on how to use the SensewearPro® and record their daily sleep diaries.

- Baseline Weeks (Weeks 1 and 5). Participants will complete three observation visits during the Baseline weeks on Monday, Wednesday, and Friday. The visits on Monday and Wednesday will last approximately 20 minutes. The start of the first phase can be scheduled within 2 days of the Intake but no more than 30 days can elapse between Intake and start of the first phase. At the observation visits participants will:
 1. Arrive at CIRNA and provide a CO and BrAC sample (Participants must have BrAC readings less than 0.01 in order to be eligible for the study).
 2. Provide a blood pressure sample (See Blood Pressure Procedures under Screening/covariate measures).
 3. Complete questionnaires (smoking rate, concomitant medication review, sleep, withdrawal, smoking urges, mood, and side effects).
 4. Have sleep diaries collected and data stored on armband downloaded by research technician. Research staff will review adherence.

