At the first (Monday) visit of Baseline Week 1 and 5, the participant will receive his or her SensewearPro® armband. At Baseline Week 1, the participant will receive an instructional packet and a research staff member will review how to use the armband and charger correctly.

The third (Friday) visit of each Baseline Week will last approximately 40 minutes. During this visit, subjects will:

1. Provide urine specimens for drug and (if applicable) pregnancy tests (Friday visit only). Participants who test positive for either the urine drug screen and/or pregnancy test will be withdrawn from the study.

2. Meet with a smoking cessation counselor for a 20-min coaching session to prepare them for the practice quit attempt. The counselor will review coping strategies for managing triggers and withdrawal symptoms.
3. Participants will receive their study medication and nicotine patches. Study staff will review instructions for taking the study medication and applying the nicotine patches.

These sessions can be scheduled for any time of day. Ideally, the subsequent sessions would be at the same time of day, but can be scheduled up to 3 hours earlier or later. However, the sessions may go beyond 3 hours as determined by PI discretion.

- Quit Assessment Weeks (Weeks 2 and 6). Participants will attend a 20 minute study visit every weekday of their quit assessment week. They will be asked to bring their study medication to this visit to verify medication adherence/pill counts. During this session, which will last approximately 20 minutes, participants will complete measures of:
 1. Blood pressure (See Blood Pressure Procedures under Screening/covariate measures)
 2. CO breath sample
 - a. To increase abstinence motivation, participants will receive \$10/day (in cash) for each day for self-reported abstinence that is biochemically-confirmed. On Monday, a CO reading of less than 10ppm or less than 50% of CO breath sample taken during the Baseline week will be sufficient as biochemically-confirmed abstinence. At all other visits, a CO reading less than 5 ppm will be considered as biochemically-confirmed abstinence.
 3. BrAC sample
 4. Smoking rate (timeline followback; TLFB)
 5. Medication adherence (pill count)
 6. Side effects and concomitant medication review
 - a. If moderate to severe adverse events are reported, the PI/Study Physician will be consulted and a decision will be made as to whether to proceed with the study.

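### The self-run pregnancy test tells staff whether the participant wishes to continue, which conflicts with the rules requiring a negative result before study medication

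*Combined protocol and SAP*

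**What the plan says.** The Urine Pregnancy Test paragraph of section 3.1 is the only place that describes how the test is done. It applies at Intake and on the Friday of weeks 1 and 5. The woman is given a CLIA-waived kit and told that "pregnant women are not advised to participate in this research study". Then: "Participants will then be instructed to administer the pregnancy test independently". Afterwards participants "will inform study staff if they would like to continue participation after they have administered the pregnancy screen". The paragraph adds that stopping at this point carries no penalty and that travel for the visit is still reimbursed.

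Elsewhere the protocol treats pregnancy as an absolute bar:

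- Key Exclusion Criteria (Medical, item 1) excludes pregnant women, and Vulnerable Populations says that none are included.
- Study Visits, Intake, item 3: "Participants who test positive for either the urine drug screen and/or pregnancy test will be ineligible".
- Study Visits, Baseline Weeks, Friday item 1, withdraws anyone who tests positive.
- Tissue Specimens (Urine) repeats that a positive pregnancy test makes a woman ineligible.
- Potential Study Risks (Pregnancy) rules out ramelteon in pregnancy. It requires women of child-bearing potential to have tested negative at Intake and again before study medication in each period.

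**The concern.** The strict rules turn on a test result. The described procedure ends with a statement of preference. A positive result and a wish to continue are compatible, and on that combination section 3.1 gives staff nothing to act on. It also presents as advice what the other sections state as a prohibition.

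The consequence would be that a woman with a positive test receives blinded study medication and nicotine patches. Treatment order is randomized and blinded, so staff cannot know which of the two hand-outs contains ramelteon, and the check has to work at both. Relying on women to withdraw themselves is weaker than checking a result. The Subject Compensation table pays up to $592 for completing the study, against travel reimbursement for a woman who stops at the test. That does not show that anyone would conceal a result. It is a reason not to rest the rule on a stated wish.

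**Working it through.** No arithmetic decides this point, and the plan gives no figure to reproduce. The check sets the sections on pregnancy testing side by side.

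1. **When the test is done.** Section 3.1 and the schedule of activities give Intake, Friday of week 1 and Friday of week 5: 1 + 1 + 1 = 3 tests per woman to whom it applies. Two of the three fall at visits where medication and patches are handed out. Tissue Specimens instead says that urine for drug and pregnancy screening is needed at every session, which does not match.

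2. **Where the result is needed at Intake.** The sequence after the eligibility items opens "Otherwise, if a participant meets the above eligibility criteria at the Intake" and leads to item 14, "Be randomized to receive RAM or PLA during the first phase". The checkpoint exists and stands ahead of randomization. It needs the result as its input.

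3. **Where the result is needed on the Fridays.** Item 1 begins "Provide urine specimens for drug and (if applicable) pregnancy tests (Friday visit only" and goes on to withdrawal for a positive test. Hand-out is item 3. The order is right, and again the step works only if someone on staff knows the result.

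4. **What reaches staff.** Section 3.1 names one communication from participant to staff after the test: whether she wishes to go on. It does not mention the result, and it does not forbid staff from seeing it.

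5. **Comparison with the neighbouring paragraph.** For the drug screen, "results from urine drug screening will not be shared with participants"; participants learn only whether they remain eligible. Staff must therefore hold that result. The pregnancy paragraph has no matching statement.

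6. **Evidence pointing the other way.** The Intake and Friday steps speak of urine specimens being provided for both tests. The Privacy list includes urine for the pregnancy test and, in general terms, test results. These lines suggest that staff may have the specimen or the result. None says who reads the pregnancy test or where the reading is entered, and a specimen handed to staff does not fit a test that the participant runs alone.

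7. **Outcome.** If staff test the urine, the visit steps contradict section 3.1. If the participant tests herself and reports only a wish, the strict rules lack their input. The text needs correcting on either reading.

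**The case against.** The strongest reply is that nothing is missing in substance. Section 3.1 does not say that the wish to continue is all that staff learn. The visit steps name the drug and pregnancy tests in the same sentence and attach exclusion or withdrawal directly to a positive result, which presupposes that staff know it. Who reads a kit, and on which form, is ordinarily left to site procedures. Section 4.1 requires source documents for case report form data and staff training on session procedures, and it has the Project Manager, the principal investigator and the Study Physician confirm eligibility together. The consent text was not available to us and may say more. Self-administration may also have been chosen for privacy or CLIA reasons.

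Much of this stands. A reader might infer that the plan permits dosing in pregnancy, or that results never reach staff and go unrecorded. The documents do not support either inference. The bar is stated in several places, its checkpoints are in the right order, and the specimen and results wording makes some staff access plausible.

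What the reply does not remove is the conflict. The one paragraph that gives operating instructions softens a prohibition into advice and ends with a preference. Section 4.1 does not mention the pregnancy test, and site practice cannot be assumed to override the protocol's own instruction.

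**Conclusion.** The point holds as an inconsistency between sections and is minor. Under section 3.1 as written, a woman who tests positive and wants to continue could be given study medication, contrary to the rules in the exclusion criteria, visit steps, tissue-specimen section and risk section.

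Several things limit the risk. The risk section reports the animal toxicity at doses far above the human dose. Medication lasts one working week per period, and only one of the two periods contains ramelteon. Women who plan a pregnancy are excluded, and contraception is agreed in writing. For harm to follow, a woman would have to test positive, wish to continue after being told it is inadvisable, and not disclose the result.

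The size cannot be put as a headcount. The documents give neither the number of women of child-bearing potential nor a rate of positive tests. Counting every woman tested as affected would overstate the problem. No endpoint, sample-size figure or analysis depends on this point. The conclusion assumes that the consent text does not already settle who reads the test.

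**What to change.** In the Urine Pregnancy Test paragraph of section 3.1:

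- Replace the advisory wording with a statement that pregnant women may not participate.
- Add, after the self-administration sentence: *The participant shows the completed test to study staff, who record it as negative, positive or invalid. An invalid test is repeated. The result is recorded before randomization at Intake, and before medication and patches are handed out on Friday of weeks 1 and 5. Hand-out follows only a recorded negative.*

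The test should be shown, because a verbal report would leave the result unverified. Self-administration and the penalty-free exit can both stay: a woman may leave without showing the test, but one who continues must show it.

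Then align the related text. Reword the specimen steps in Intake item 3 and Friday item 1 to match a self-run test that staff read. Correct Tissue Specimens so that drug and pregnancy screening is tied to Intake and the two Fridays and not to all sessions. The exclusion and withdrawal rules can stay as they are, with a cross-reference.

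The cost is a few wording changes and one source-document field. No test or visit is added. The downsides are slightly less privacy for the participant and a check that staff reading and recording a CLIA-waived kit fits the site's CLIA arrangements.

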Transdermal Nicotine (TN) Replacement Therapy: All participants will receive transdermal nicotine (TN) patch therapy to aid in quitting smoking. This therapy is available over the counter and is very well tolerated. Participants will use the 21 mg patch for 5 days during each quit assessment week. Nausea, vomiting, weakness, dizziness, and rapid heartbeat occur rarely and are most often caused by continuing to smoke while using the patch. In addition, there is a risk of peptic ulcer formation and delayed wound healing associated with nicotine replacement therapies. Some individuals who use the patch experience minor skin irritation, such as redness, rash, or minor swelling, and insomnia and dream abnormalities. Because sleep problems are a primary mechanism of interest, participants will be instructed to remove the patch during the night while sleeping to avoid dream abnormalities. All of these reactions cease once the patch is removed.

During the third visit of each baseline week (weeks 1 and 5), a member of the research staff will review the purpose of using the nicotine patch (e.g., to help manage withdrawal symptoms; not a substitute for behavioral quitting strategies), provide directions on how to use the patch (e.g., abstinence from smoking, patch location, time, activity, and potential skin reactions), and answer any questions.

Because increased blood pressure is a side effect of TN patch therapy, blood pressure will be closely monitored at each visit. Expanding the upper limit of the blood pressure to less than 160/100 does not increase the risk to subjects enrolled in this trial. The risk of increased blood pressure is no greater than the risk from smoking and quitting smoking will lower an individual's risk. If a participant presents with a SBP between 151-159 mmHg and/or DBP between 91-99 mmHg at the Intake or Pre-Quit visit, the research staff will inform the participant that they have mild, Stage I, hypertension and advise they consult with a physician. The participant will remain eligible for the study and receive nicotine patches as scheduled.

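### After a confirmed post-Intake blood pressure reading above 159/99, the protocol holds the study medication (most likely the capsule) but gives no instruction for the nicotine patch, the product it links to blood pressure

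*Combined protocol and SAP*

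**What the plan says.** The transdermal nicotine paragraphs under Risk/Benefit Assessment, 1. Potential Study Risks, make the link between product and sign: "Because increased blood pressure is a side effect of TN patch therapy, blood pressure will be closely monitored at each visit".

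The action rule is in section 3.1, Screening/Covariate Measures, under Blood Pressure. It applies at every in-person visit after Intake. If the systolic value is still above 159 mmHg and/or the diastolic above 99 mmHg on the third reading, "the subject will be told to not take the next dose of study medication". The rule does not mention the patch.

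The same paragraph then describes a milder band, 151-159 and/or 91-99. It ends with a sentence under which the Study Physician or Health Care Provider is notified and "will review the blood pressure reading and determine whether it is safe for the subject to continue".

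The term *study medication* is not defined. In section 2, Study Visits, the Baseline Friday visit treats the two products separately: "Study staff will review instructions for taking the study medication and applying the nicotine patches". For the quit weeks the same section ties the term to pills: "They will be asked to bring their study medication to this visit to verify medication adherence/pill counts".

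**The concern.** Blood pressure is measured at each visit because of the patch, but the one product action attached to a confirmed high reading appears to fall on the capsule. The ramelteon side effects listed under Potential Study Risks, common and rare, do not include raised blood pressure. Staff who follow the rule literally would therefore hold the product with no listed blood pressure effect and have no instruction for the 21 mg patch.

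What is at stake is the participant's safety between a confirmed reading above 159/99 and a physician's decision. The same confirmed level at Intake makes a person ineligible, so the sponsor already treats it as too high to begin the trial.

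**Working it through.** No arithmetic applies. The check is a side-by-side reading.

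1. **Which product is linked to blood pressure?** The patch, by the protocol's own statement in Potential Study Risks. Blood pressure is absent from the ramelteon lists in the same section.

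2. **What does *study medication* mean in the rule?** Four places point to the capsule.
   - Drugs or Devices, Ramelteon: study medication is taken shortly before bed.
   - Section 2, Study Visits: it is taken whereas patches are applied, and it is checked by pill count.
   - Schedule of activities: ramelteon/placebo and transdermal nicotine have separate rows. Only the ramelteon/placebo row carries the footnote saying that study medication was taken the night before.
   - Potential Study Risks, on ramelteon: the bedtime instruction is repeated for study medication. The patch, in contrast, is removed for the night.

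   Two places use *medication* more broadly: the medication row of Figure 1, which pairs each treatment with the patch, and section 4.3, where reducing or stopping medication is discussed for ramelteon and nicotine together. A wider meaning is therefore possible but less likely.

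3. **What follows at a quit-week visit?** On the likelier meaning, the next capsule is held and the patch has no instruction. On the wider meaning, the next patch is held too, but nothing is said about the patch being worn at the visit.

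4. **What follows at the Baseline Friday visit?** Capsules and patches are handed out at this visit, and the patch is to start on the morning of the target quit date. After a confirmed reading above 159/99 here, the rule on its likelier meaning holds the first capsule of the coming week. Nothing tells staff to withhold the patches or tells the participant not to start them.

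5. **Does the protocol write patch rules elsewhere?** Yes. Potential Study Risks tells participants to stop the patch promptly for severe or persistent skin reactions. The 151-159/91-99 text says that patches are given as planned. The band above 159/99 is the one left without a patch instruction.

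6. **What other text could supply the missing instruction?**
   - Section 3.1, closing physician-review sentence: probably covers these readings, but does not say so and does not mention the patch.
   - Section 2, quit-week visit list: the investigator or Study Physician is consulted when moderate to severe adverse events are reported.
   - Section 4.2: the adverse event definition could take in a clinically significant abnormal finding.
   - Section 4.3: a notable medical concern goes to the Project Manager, Study Physician and Principal Investigator, who choose a course of action.
   - Potential Study Risks, on the patch: significant side effects are evaluated by the study physician, who may lower the dose or recommend stopping.
   - Section 4.1: forms holding blood pressure values are reviewed on an ongoing basis.

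   Each is a route to a decision about the patch. None states a blood pressure value that triggers action on it.

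**The case against.** The strongest reply is that a physician would decide in any case. The closing sentence of the Blood Pressure paragraph ends the paragraph that contains the rule, and it would be odd to require review at 151-159 but not above 159. In a trial where everyone wears the patch, deciding whether it is safe to continue naturally takes in the patch. Adverse-event consultation applies at the very visits concerned, blood pressure is rechecked every weekday of the quit week, and the patch comes off each night. Most of this stands. It limits the gap to the interval before a decision and rules out any claim that such readings would go unmanaged. It does not supply a patch instruction.

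A second reply is that holding the patch has a cost. It removes cessation support during a five-day quit attempt whose primary outcome is days abstinent, and it could prompt smoking. The protocol itself argues that the blood pressure risk is no greater than that of smoking. This also stands as a cost. It is a reason to keep the hold short and under physician control. It is not a reason to leave the patch unmentioned while the capsule is held.

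A reader might go further and infer that the 151-159/91-99 step is also defective because it names only readings "at the Intake or any visit during a Baseline week" and no quit-week visit. The documents do not support that. The step works as an advisory before patch use begins, it lets the patch go ahead, and the sponsor's stated position is that allowing values below 160/100 "does not increase the risk to subjects enrolled in this trial". Extending it to quit weeks would be a preference, not a correction.

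**Conclusion.** The point holds as a minor participant-safety correction. For a confirmed post-Intake reading above 159 and/or 99, the only explicit product instruction most likely concerns the capsule, while the product that the protocol ties to blood pressure has none. This is a misdirected rule and not merely missing detail, but several general safeguards soften it.

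The conclusion rests on one reading: that *study medication* means the capsule. That fits most of the protocol's usage but is not defined. If the wider meaning was intended, what remains is smaller, namely the patch already on, which is removed at bedtime.

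The documents give no frequency for such readings, so no number of participants or of patch-days is claimed. A reader might also infer that the trial's results are at risk. Nothing in the plan supports that: sample size and analysis are unaffected.

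**What to change.** Amend the Blood Pressure paragraph of section 3.1 in three respects:

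- After a confirmed post-Intake reading above 159 and/or 99, the patch as well as the capsule is held, or not started if the reading falls in a Baseline week, pending same-day Study Physician review. The physician then decides for each product whether it resumes.
- State that the closing notification sentence covers these readings and that the decision includes the patch.
- State that a hold directed by staff does not count as a missed dose under General Exclusion item 7, which concerns two or more missed doses. The current rule already leaves that question open.

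The cost is a wording amendment, some physician calls on the same day, and an occasional brief loss of patch support during a quit attempt. No new visit, device or measurement is needed.
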